7.4 Study stopping rules

Enrollment will be put on hold pending full safety review if more than one unexpected and possibly related SAEs is reported. The study will be stopped if the benefit-risk ratio changes to be unacceptable in this indication.

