3.1 Study design

This is an open-label, non-controlled study in patients with PNH. Approximately 10 patients will be enrolled in the study. At the time that Protocol amendment v07 is effective, no additional patients will be enrolled. The study drug will be administered via i.v. infusion at the dose level of 20 mg/kg every 14 days. Patients participating in study will have an option to either complete period 3 Follow up and Study Completion evaluation or continue in study period 4 that is pre-requisite to join the long-term extension study CLNP023C12001B, that is separate to this study protocol. Patients who are potentially eligible and willing to participate in the LNP023 long-term extension study will join period 4, where treatment will be converted from LFG316 to LNP023 200 mg b.i.d.

The study will consist of a 60-day screening period to assess eligibility and conduct vaccinations if required (for all patients not previously vaccinated at least 2 weeks prior to first dosing or if prior vaccination cannot be confirmed). An extensive screening window (up to 60 days) is planned in order to comply with local vaccination requirements, if available and deemed necessary at the investigator's discretion. Safety evaluation assessments requiring blood and urine samplings, pregnancy test, pulmonary function test, ECG, patient reported outcomes, and assessment of number of blood transfusions should be performed no longer than 4 weeks prior

to the planned dosing day. Subjects who meet the eligibility criteria at screening will be admitted to baseline (Day 1) evaluations. The patients will enter treatment period 1, and will receive infusions of LFG316 every 14 days, days 1, 15 and 29 (3 administrations).

At the end of period 1, efficacy on hemolytic activity by serum LDH will be assessed. All patients will then be allowed to enter the optional treatment period 2, and will receive infusions of LFG316 every 14 days, and undergo the efficacy, PK, CCI and safety assessments for additional 48 weeks.

Following the 48-week treatment period 2, LFG316-responsive patients (assessed based on investigator's judgment) will be allowed to enter an additional third extension period of up to 260 weeks (extension period 3).

The LFG316 treatment for all patients will be completed by end of 2021 regardless of each individual treatment period.

[figure not shown]

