Patients participating in extension period 3 will roll over from the last dosing visit of period 2 to the first visit (which includes drug administration) of period 3. The same dosing interval applied in Period 1 and 2 will be applied between the last dosing visit of Period 2 and the first visit of Period 3.

Period 4 can be initiated as directed by Sponsor and will last approximately 21 weeks. During the first 4 weeks patients will continue to receive LFG316 20 mg/kg every two weeks (total of two administrations) in addition to oral administration of LNP023 200 mg b.i.d. After 4 weeks, patients will discontinue LFG316 and will proceed with LNP023 200 mg b.i.d. monotherapy for approximately 16 weeks (+/- 28 days). Patients who participate in period 4 can join the long-term extension study CLNP023C12001B as soon as their eligibility is confirmed and study CLNP023C12001B is open to receive patients. There should be no LNP023 treatment gap between the studies. Please refer to [Section 7.1](#) for guidance regarding safety monitoring and LNP023 down-titration in case of LNP023 treatment discontinuation.

Commercially Confidential Information

For patients not participating in the period 4, the extension period 3 will be followed by a Study Completion evaluation approximately 8 weeks after the last drug administration. Patients who discontinue treatment prematurely during any of the study periods will be followed for 8 weeks after discontinuation, and will similarly undergo a study completion visit. The 8 weeks follow-up period will start the day after the last drug administration (both for patients completing treatment and patients prematurely discontinuing), and will comprise one visit after approximately 4 weeks, and a study completion visit after approximately 8 weeks from the last drug administration. Safety assessments will include physical examinations, ECG, vital signs, standard clinical laboratory evaluations (hematology, blood chemistry, urinalysis) and adverse event monitoring.

Patients participating in period 4, will complete their Study Completion evaluation approximately one week after last LNP023 treatment administered as a part of this study.

Figure 3-1 Study design

*Period 4 is applicable only for the patients who are potentially eligible and wish to participate in the long-term extension study CLNP023C12001B

**+/-28 days

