Based on its mechanism of action, the main potential risk of LNP023 is infection-related. An intact complement system is particularly important for the defense against encapsulated bacteria (e.g., *Neisseria meningitidis*, *Streptococcus pneumoniae*, and *Hemophilus influenzae*). Patients with factor B loss-of-function mutations are more susceptible to such infections ([Slade et al 2013](#)). The mitigation strategy is to vaccinate patients before the first LNP023 treatment. If LNP023 treatment has to start earlier than 2 weeks post vaccination, prophylactic antibiotic treatment must be initiated. Data suggest that the protective effect of vaccination is maintained after blockade of the AP, but not after C5 blockade ([Konar and Granoff 2017](#)). In addition, patients will be instructed to contact the Investigator immediately in case of any signs or symptoms of infection (listed on a “Patient Card” for participant awareness), and relevant AEs will be reviewed on a regular basis.

Commercially Confidential Information

Regarding the potential safety risks mentioned above, to date, there have been no serious infections reported in PNH patients, although a SUSAR of pneumococcal pneumonia and sepsis was recently reported on the C3 glomerulopathy trial in a severely immunosuppressed patient with a history of renal transplantation (see [Section 1.1.1.3.2](#)). Considering implementation of the vaccinations and close monitoring, the risk for serious infection during LNP023 treatment is still considered to be low. Finally, there have been no serious adverse events related to the other potential risks in any of the clinical studies.

Commercially Confidential Information

Commercially Confidential Information

The risk to subjects in this trial receiving LNP023 will be minimized by adherence to the eligibility criteria, close clinical monitoring, pre-defined stopping rules, periodic review of the safety data, and guidance for the investigators in the Investigator's Brochure.

To note, women of child bearing potential (WOCBP) must be informed that taking the study treatment may involve unknown risks to the fetus if pregnancy were to occur during the study, and agree that in order to participate in the study they must adhere to the highly effective contraception requirements outlined in the Exclusion Criteria. If there is any question that the subject will not reliably comply, they should not be entered or continue in the study.

4 Population

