9.6 Early phase safety monitoring

The Investigator will monitor adverse events in an ongoing manner and inform the Sponsor of any clinically relevant observations. Any required safety reviews will be made jointly between medically qualified personnel representing the Sponsor and Investigator. Such evaluations may occur verbally, but the outcome and key discussion points will be summarized in writing (e-mail) and made available to both Sponsor and all Investigator(s). Criteria pertaining to stopping the study/treatment or adapting the study design are presented above.

The Sponsor will advise all the participating the Investigators at all sites in writing (e-mail) (and by telephone if possible) of any new, clinically relevant safety information reported from another site during the conduct of the study in a timely manner.

10 Data review and database management

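### Potential Hy's Law has two definitions that disagree when baseline bilirubin is raised, and the only visible SAE-count rule holds an enrolment that is already closed

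*Protocol*

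**What the plan says.** **Potential Hy's Law.** Both definitions require ALT or AST above 3xULN without ALP rising above 2xULN. They differ on bilirubin:

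- Protocol Table 9-1: TBL above 2xULN, mainly the conjugated fraction. Baseline plays no part.
- Protocol Table 9-2, footnote a: TBL above 2xULN if baseline was normal, or above twice baseline if baseline was raised. The fraction plays no part.

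The Table 9-2 row attached to footnote a requires a check of the bilirubin fraction and an immediate drug stop if haemolysis cannot explain the rise. Section 8.3.4 notes that bilirubin is often raised in PNH.

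**SAE-count rule.** Section 7.4: "Enrollment will be put on hold pending full safety review if more than one unexpected and possibly related SAEs is reported". Section 3.1: "At the time that Protocol amendment v07 is effective, no additional patients will be enrolled". For period 4, Section 3.6.1 says that LNP023 risk will be "minimized by adherence to the eligibility criteria, close clinical monitoring, pre-defined stopping rules, periodic review of the safety data". Section 9.6 provides for joint sponsor and investigator safety review without a numeric trigger, and adds: "Criteria pertaining to stopping the study/treatment or adapting the study design are presented above". On timing, Section 3.1 says "Period 4 can be initiated as directed by Sponsor and will last approximately 21 weeks" and also "The LFG316 treatment for all patients will be completed by end of 2021 regardless of each individual treatment period".

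**Follow-up after an early LNP023 stop.** Section 3.1: "Patients who discontinue treatment prematurely during any of the study periods will be followed for 8 weeks after discontinuation", with visits at about 4 and 8 weeks from the last drug administration. The general text of Section 7.1 also asks for the 8 weeks where it can be done. Section 3.1 then says: "Patients participating in period 4, will complete their Study Completion evaluation approximately one week after last LNP023 treatment". The LNP023 text of Section 7.1 and the period 4 schedule agree with the one-week visit. Section 7.2 adds a safety call at about 30 days for patients who do not roll over.

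**The concern.** A liver rule has to give the same answer whichever table the site opens. Here the tables part company in patients with raised baseline bilirubin, who are expected in this disease. What is at stake is whether the drug must be stopped at once when haemolysis does not explain the rise, or whether the site repeats the test and stops at its discretion.

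The Section 7.4 hold was sensible while patients were being enrolled. Under the current protocol the only new exposure is conversion to LNP023 in period 4, and the hold does not reach it, although Section 3.6.1 counts stopping rules among the protections for that period.

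The follow-up wording is a smaller matter. A site could read either duration for a patient who stops LNP023 early, and Section 3.3.2 itself recognises a possible increase in haemolysis after LNP023 is stopped.

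**Working it through.** The plan gives no figure to reproduce on these points. The check sets the texts side by side and applies them to assumed patients.

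**1. The two Hy's Law definitions.** Values are multiples of ULN. Assumed throughout: ALT 4, ALP 1, INR at most 1.5, no symptoms, no jaundice, and mainly conjugated read as more than 50%.

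- Rule A (Table 9-1): TBL > 2.0 and conjugated/TBL > 0.5.
- Rule B (footnote a): TBL > 2.0 if baseline is normal; TBL > 2 x baseline if baseline is raised.

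| Assumed patient | Rule A | Rule B |
|---|---|---|
| Baseline 1.5; on study 2.5, of which 1.5 conjugated | 2.5 > 2.0 and 1.5/2.5 = 0.60: case | needs > 2 x 1.5 = 3.0: not a case |
| Baseline 1.5; on study 3.2, of which 1.5 conjugated | 1.5/3.2 = 0.47: not a case | 3.2 > 3.0: case |

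For a mainly conjugated rise, the two rules agree when baseline is normal (both thresholds are 2.0). When baseline is raised, the values that meet A but not B lie above 2.0 and up to 2 x baseline:

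| Baseline | Upper end of the gap |
|---|---|
| 1.2 | 2 x 1.2 = 2.4 |
| 1.5 | 2 x 1.5 = 3.0 |
| 1.8 | 2 x 1.8 = 3.6 |
| 2.0 | 2 x 2.0 = 4.0 |

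**2. What happens to the first patient.** The Hy's Law row of Table 9-2 is not reached. The isolated-bilirubin row does not apply, because ALT is raised and TBL is not above 3. What applies is the row for asymptomatic ALT above 3 and up to 5: repeat liver tests within a week and, if confirmed, observe closely. Table 9-1 still makes TBL above 2xULN a liver event (no Gilbert syndrome, not attributed to haemolysis). Section 9.3 then asks for repeat tests, causality assessment and investigation to resolution, with discontinuation and hospital admission if appropriate. The loss is therefore specific: an obligatory stop becomes a discretionary one.

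**3. The second patient.** This one enters the Hy's Law row, which checks the fraction and stops the drug only if haemolysis does not explain the rise. The mismatch in this direction has little effect.

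**4. The SAE-count rule.** Trigger: more than one unexpected, possibly related SAE. Action: hold enrolment. Enrolments left to hold after amendment v07: none. New period 4 starts paused by the rule: none.

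A redirected hold has a calendar limit. The period 4 schedule gives LFG316 on days 1 and 15, and LFG316 ends with 2021. Latest day 1 = 31 December 2021 - 14 days = 17 December 2021.

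**5. Follow-up after an early LNP023 stop.** Counted from the last drug administration, taken as the LNP023 stop: last visit at 8 x 7 = 56 days or at 7 days, a difference of 49 days. Last contact is at 56 days or at about 30 days, a difference of about 26 days.

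**The case against.** **Hy's Law.** Section 9.3 sends the reader to both tables for the definitions, so they are meant to be used together. That does not say which prevails when they disagree. The gap is also narrow: symptoms with ALT above 3xULN, INR above 1.5, ALT above 8xULN, or jaundice not attributed to PNH each bring an immediate stop by another row. All of that stands. A reader might infer that a patient in the gap would get only a repeat test and stay on drug. The documents do not support this, because the patient remains a liver event under Table 9-1 with the Section 9.3 actions.

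**SAE-count rule.** A reader might infer that period 4 has no stopping protection. That is not so. Section 7.4 also stops the study if benefit-risk becomes unacceptable, Section 7.5 lets the sponsor terminate for safety, the sponsor directs when period 4 starts, Section 9.6 provides joint review, and Section 7.1 and Table 9-2 contain patient-level stops. Section 3.6.1 does not say that its stopping rules are counted or study-level, so the patient-level rules may be what it means. Sections 3.5 and 11.8 are blacked out and could hold more. The rule is therefore inoperative rather than wrong. What stands is that no visible count-based trigger reaches new LNP023 exposure.

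**Follow-up.** A reader might infer two competing schedules of equal standing. In context, the 8-week sentence sits in a paragraph that opens with patients who do not enter period 4, and period 4 then has its own paragraph. The period 4 text is consistent with itself, and Section 7.2 ties the 8 weeks to patients ending after period 3. Nor are early stoppers left unprotected: Section 7.1 recommends prompt standard of care, close monitoring for haemolysis, and weekly visits during a taper. What remains is that the 8-week sentence literally covers every period, and that the general line in Section 7.1 makes no exception for LNP023.

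**Conclusion.** **Main point, wrong as written.** The two definitions of a potential Hy's Law case conflict. With raised baseline bilirubin, a mainly conjugated TBL above 2xULN and up to twice baseline meets Table 9-1 and misses the Hy's Law row of Table 9-2. The effect is loss of the mandatory immediate stop when haemolysis cannot explain the rise, not loss of all action. The example values are assumed; the documents do not say how many patients would fall in the gap.

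**Second point, inoperative.** The only visible SAE-count rule can pause nothing once amendment v07 is effective, while period 4 exposes patients to LNP023 under a text that cites stopping rules. Judgement-based and patient-level safeguards remain.

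**Third point, clarification only.** The follow-up texts leave a 49-day difference in the last visit open to reading.

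These are safety instructions. The week-4 LDH responder definition and the proof-of-concept criterion do not change. Worth fixing, because each correction is a matter of wording.

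**What to change.** One amendment can carry all three changes.

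- **Hy's Law.** Apply the potential Hy's Law row of Table 9-2 if either definition is met. That row already checks the fraction and spares patients whose rise is due to haemolysis. Cost: a few more fraction checks.
- **SAE-count rule.** If more than one unexpected SAE possibly related to LNP023 or LFG316 is reported, pause new period 4 starts pending a prompt, documented review under Section 9.6. Both drugs should count because they are given together for the first four weeks. Patients who are waiting stay on LFG316 every 14 days. The review must decide in time for day 1 to fall by 17 December 2021, so that both overlap infusions can be given. Cost: a possible short delay to conversion.
- **Follow-up.** State which schedule applies to patients who stop LNP023 early and do not roll over. Preferably keep the one-week visit and add LDH at 4 and 8 weeks from the last drug administration. Cost: two further visits for each such patient.

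No new patients are needed, and the primary analysis is untouched.

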7.5 Early study termination

The study can be terminated at any time by Novartis.

Reasons for early termination:

- Unexpected, significant, or unacceptable safety risk to subjects enrolled in the study
- Decision based on recommendations from applicable board(s) after review of safety and efficacy data
- Discontinuation of study drug development

In taking the decision to terminate, Novartis will always consider subject welfare and safety. Should this be necessary, subjects should be seen as soon as possible and treated as a prematurely withdrawn subject. The investigator may be informed of additional procedures to be followed in order to ensure that adequate consideration is given to the protection of the subject's interests. The investigator or sponsor will be responsible for informing IRBs/IECs of the early termination of the trial depending on local regulation.

8 Procedures and assessments

Subjects should be seen for all visits on the designated day, with the assessments performed as per schedule, within the allowed "visit/assessment window" specified in the Site Operations Manual.

If the COVID-19 pandemic limits or prevents on-site study visits, alternative methods of providing continuing care may be implemented. Phone calls, virtual contacts (e.g. teleconsultation) or visits by site staff/home nursing service to the patient's home depending on local regulations and capabilities, can replace on-site study visits, for the duration of the pandemic until it is safe for the patient to visit the site again. Local laboratory to monitor safety might be implemented if feasible.

Table 8-1 Assessment schedule

Study epoch	Screening	Treatment																													
		Treatment Period 1												Treatment Period 2 (Extension Period 2)																	
Study phase Visit Numbers (internal use only)	Screening	1	101	102	103	104	105	201	202	203	204	205	206	207	208	209	210	211	212	213	214	215	216	217	218	219	220	221	222	223	224
	V1	V2	V3	V4	V5	V6	V7	V8	V9	V10	V11	V12	V13	V14	V15	V16	V17	V18	V19	V20	V21	V22	V23	V24	V25	V26	V27	V28	V29	V30	
Day	D-60* to 0	D1	D8	D15	D22	D29	D43	D57	D71	D85	D93	D113	D127	D141	D155	D169	D183	D197	D211	D225	D239	D253	D267	D281	D295	D303	D323	D337	D351	D365	
Inclusion /Exclusion criteria	X																														
Relevant med. History/Current conditions	X																														
Demography	X																														
Physical examination	X	X	X	X	X	X	X		X			X			X			X			X		X		X		X		X		
HIV screen	X																														

Commercially Confidential Information

Urine drug screen & alcohol test	X	X																											
Vaccination (for all patients not previously vaccinated at least two weeks prior to first dosing or if prior vaccination cannot be confirmed)	X																												
Pregnancy test	X ^a	X				X		X		X		X		X		X		X		X		X		X		X		X	
Drug administration		X		X		X	X	X	X	X	X	X	X	X	X	X	X	X	X	X	X	X	X	X	X	X	X	X	
Adverse Events																													
Concomitant meds/Therapies	X																												
Comments																													
Vital signs and body measurements																													
Body height	X																												
Body weight	X		X			X		X		X		X		X		X		X		X		X		X		X		X	
Body temperature	X	X	X	X	X	X	X	X	X	X	X	X	X	X	X	X	X	X	X	X	X	X	X	X	X	X	X	X	
Blood pressure / Pulse rate	X	X	X	X	X	X	X	X	X	X	X	X	X	X	X	X	X	X	X	X	X	X	X	X	X	X	X	X	
ECG evaluation	X	X		X		X		X		X		X		X		X		X		X		X		X		X		X	
Safety Laboratory Evaluations: Hematology (including Reticulocyte counts), Blood chemistry (including serum LDH, free Hgb and haptoglobin)	X	X	X	X	X	X	X	X	X	X	X	X	X	X	X	X	X	X	X	X	X	X	X	X	X	X	X	X	
Urinalysis	X	X	X	X	X	X	X	X	X	X	X	X	X	X	X	X	X	X	X	X	X	X	X	X	X	X	X	X	
Number of blood transfusions	X	X	X	X	X	X	X	X	X	X	X	X	X	X	X	X	X	X	X	X	X	X	X	X	X	X	X	X	
PNH type III RBCs by flow cytometry	X																												
Pulmonary Function Test		X				X		X		X		X		X		X		X		X		X		X		X		X	

Commercially Confidential Information

PK blood collection		X ^b	X	X ^b	X	X ^b	X ^c																		
---------------------	--	----------------	---	----------------	---	----------------	----------------	----------------	----------------	----------------	----------------	----------------	----------------	----------------	----------------	----------------	----------------	----------------	----------------	----------------	----------------	----------------	----------------	----------------	----------------

Commercially Confidential Information

a: Serum pregnancy test required at screening, urine pregnancy test at further time points. Only for post-menopausal women, the hormone measurement (FSH) to confirm post menopausal status required at screening

b: Samples collected pre- and post dose - Post-dose PK samples must be collected only upon infusion completion, and within 2 hours of the end of the infusion

c: Samples collected pre- dose

d: sample to be collected at baseline or at any visit post baseline

* Screening period to enable the conduct of vaccination requirements (if local guidelines requires it, and if deemed necessary at investigator's discretion)

Study epoch		Treatment (continued)																																																																																																																																																																																																																																																																																																																																																																																																																																																																																																																																																																																																																																																																																																																																																																																																																																																																																																																																																																																																																																																																																																																																																
Study phase		Treatment Period 3 (Extension Period 3)																																																																																																																																																																																																																																																																																																																																																																																																																																																																																																																																																																																																																																																																																																																																																																																																																																																																																																																																																																																																																																																																																																																																																
Visit Numbers (internal use only)		301	302	303	304	305	306	307	308	309	310	311	312	313	314	315	316	317	318	319	320	321	322	323	324	325	326	327	328																																																																																																																																																																																																																																																																																																																																																																																																																																																																																																																																																																																																																																																																																																																																																																																																																																																																																																																																																																																																																																																																																																																					
1st Year Extension	V41	V42	V43	V44	V45	V46	V47	V48	V49	V50	V51	V52	V53	V54	V55	V56	V57	V58	V59	V60	V61	V62	V63	V64	V65	V66	V67	V68	V69																																																																																																																																																																																																																																																																																																																																																																																																																																																																																																																																																																																																																																																																																																																																																																																																																																																																																																																																																																																																																																																																																																																					
	Week	54	56	58	60	62	64	66	68	70	72	74	76	78	80	82	84	86	88	90	92	94	96	98	100	102	104	106	108	110																																																																																																																																																																																																																																																																																																																																																																																																																																																																																																																																																																																																																																																																																																																																																																																																																																																																																																																																																																																																																																																																																																																				
	Day	379	393	407	421	435	449	463	477	491	505	519	533	547	561	575	589	603	617	631	645	659	673	687	701	715	729	743	757	771	785	799	813	827	841	855	869	883	897	911	925	939	953	967	981	995	1009	1023	1037	1051	1065	1079	1093																																																																																																																																																																																																																																																																																																																																																																																																																																																																																																																																																																																																																																																																																																																																																																																																																																																																																																																																																																																																																																																																																													
2nd Year Extension	Visit Numbers (internal use only)	401	402	403	404	405	406	407	408	409	410	411	412	413	414	415	416	417	418	419	420	421	422	423	424	425	426	427	428	429	430	431	432	433	434	435	436	437	438	439	440	441	442	443	444	445	446	447	448	449	450	451	452	453	454	455	456	457	458	459	460	461	462	463	464	465	466	467	468	469	470	471	472	473	474	475	476	477	478	479	480	481	482	483	484	485	486	487	488	489	490	491	492	493	494	495	496	497	498	499	500	501	502	503	504	505	506	507	508	509	510	511	512	513	514	515	516	517	518	519	520	521	522	523	524	525	526	527	528	529	530	531	532	533	534	535	536	537	538	539	540	541	542	543	544	545	546	547	548	549	550	551	552	553	554	555	556	557	558	559	560	561	562	563	564	565	566	567	568	569	570	571	572	573	574	575	576	577	578	579	580	581	582	583	584	585	586	587	588	589	590	591	592	593	594	595	596	597	598	599	600	601	602	603	604	605	606	607	608	609	610	611	612	613	614	615	616	617	618	619	620	621	622	623	624	625	626	627	628	629	630	631	632	633	634	635	636	637	638	639	640	641	642	643	644	645	646	647	648	649	650	651	652	653	654	655	656	657	658	659	660	661	662	663	664	665	666	667	668	669	670	671	672	673	674	675	676	677	678	679	680	681	682	683	684	685	686	687	688	689	690	691	692	693	694	695	696	697	698	699	700	701	702	703	704	705	706	707	708	709	710	711	712	713	714	715	716	717	718	719	720	721	722	723	724	725	726	727	728	729	730	731	732	733	734	735	736	737	738	739	740	741	742	743	744	745	746	747	748	749	750	751	752	753	754	755	756	757	758	759	760	761	762	763	764	765	766	767	768	769	770	771	772	773	774	775	776	777	778	779	780	781	782	783	784	785	786	787	788	789	790	791	792	793	794	795	796	797	798	799	800	801	802	803	804	805	806	807	808	809	8010	8011	8012	8013	8014	8015	8016	8017	8018	8019	8020	8021	8022	8023	8024	8025	8026	8027	8028	8029	8030	8031	8032	8033	8034	8035	8036	8037	8038	8039	8040	8041	8042	8043	8044	8045	8046	8047	8048	8049	8050	8051	8052	8053	8054	8055	8056	8057	8058	8059	8060	8061	8062	8063	8064	8065	8066	8067	8068	8069	8070	8071	8072	8073	8074	8075	8076	8077	8078	8079	8080	8081	8082	8083	8084	8085	8086	8087	8088	8089	8090	8091	8092	8093	8094	8095	8096	8097	8098	8099	80100	80101	80102	80103	80104	80105	80106	80107	80108	80109	80110	80111	80112	80113	80114	80115	80116	80117	80118	80119	80120	80121	80122	80123	80124	80125	80126	80127	80128	80129	80130	80131	80132	80133	80134	80135	80136	80137	80138	80139	80140	80141	80142	80143	80144	80145	80146	80147	80148	80149	80150	80151	80152	80153	80154	80155	80156	80157	80158	80159	80160	80161	80162	80163	80164	80165	80166	80167	80168	80169	80170	80171	80172	80173	80174	80175	80176	80177	80178	80179	80180	80181	80182	80183	80184	80185	80186	80187	80188	80189	80190	80191	80192	80193	80194	80195	80196	80197	80198	80199	80200	80201	80202	80203	80204	80205	80206	80207	80208	80209	80210	80211	80212	80213	80214	80215	80216	80217	80218	80219	80220	80221	80222	80223	80224	80225	80226	80227	80228	80229	80230	80231	80232	80233	80234	80235	80236	80237	80238	80239	80240	80241	80242	80243	80244	80245	80246	80247	80248	80249	80250	80251	80252	80253	80254	80255	80256	80257	80258	80259	80260	80261	80262	80263	80264	80265	80266	80267	80268	80269	80270	80271	80272	80273	80274	80275	80276	80277	80278	80279	80280	80281	80282	80283	80284	80285	80286	80287	80288	80289	80290	80291	80292	80293	80294	80295	80296	80297	80298	80299	80300	80301	80302	80303	80304	80305	80306	80307	80308	80309	80310	80311	80312	80313	80314	80315	80316	80317	80318	80319	80320	80321	80322	80323	80324	80325	80326	80327	80328	80329	80330	80331	80332	80333	80334	80335	80336	80337	80338	80339	80340	80341	80342	80343	80344	80345	80346	80347	80348	80349	80350	80351	80352	80353	80354	80355	80356	80357	80358	80359	80360	80361	80362	80363	80364	80365	80366	80367	80368	80369	80370	80371	80372	80373	80374	80375	80376	80377	80378	80379	80380	80381	80382	80383	80384	80385	80386	80387	80388	80389	80390	80391	80392	80393	80394	80395	80396	80397	80398	80399	80400	80401	80402	80403	80404	80405	80406	80407	80408	80409	80410	80411	80412	80413	80414	80415	80416	80417	80418	80419	80420	80421	80422	80423	80424	80425	80426	80427	80428	80429	80430	80431	80432	80433	80434	80435	80436	80437	80438	80439	80440	80441	80442	80443	80444	80445	80446	80447	80448	80449	80450	80451	80452	80453	80454	80455	80456	80457	80458	80459	80460	80461	80462	80463	80464	80465	80466	80467	80468	80469	80470	80471	80472	80473	80474	80475	80476	80477	80478	80479	80480	80481	80482	80483	80484	80485	80486	80487	80488	80489	80490	80491	80492	80493	80494	80495	80496	80497	80498	80499	80500	80501	80502	80503	80504	80505	80506	80507	80508	80509	80510	80511	80512	80513	80514	80515	80516	80517	80518	80519	80520	80521	80522	80523	80524	80525	80526	80527	80528	80529	80530	80531	80532	80533	80534	80535	80536	80537	80538	80539	80540	80541	80542	80543	80544	80545	80546	80547	80548	80549	80550	80551	80552	80553	80554	80555	80556	80557	80558	80559	80560	80561	80562	80563	80564	80565	80566	80567	80568	80569	80570	80571	80572	80573	80574	80575	80576	80577	80578	80579	80580	80581	80582	80583	80584	80585	80586	80587	80588	80589	80590	80591	80592	80593	80594	80595	80596	80597	80598	80599	80600	80601	80602	80603	80604	80605	80606	80607	80608	80609	80610	80611	80612	80613	80614	80615	80616	80617	80618	80619	80620	80621	80622	80623	80624	80625	80626	80627	80628	80629	80630	80631	80632	80633	80634	80635	80636	80637	80638	80639	80640	80641	80642	80643	80644	80645	80646	80647	80648	80649	80650	80651	80652	80653	80654	80655	80656	80657	80658	80659	80660	80661	80662	80663	80664	80665	80666	80667	80668	80669	80670	80671	80672	80673	80674	80675	80676	80677	80678	80679	80680	80681	80682	80683	80684	80685	80686	80687	80688	80689	80690	80691	80692	80693	80694	80695	80696	80697	80698	80699	80700	80701	80702	80703	80704	

Commercially Confidential Information

Commercially Confidential Information

Study epoch	Treatment (continued)																											Follow-up	Study Completion		
	Treatment Period 3 (Extension Period 3)																														
Visit Numbers (internal use only)	531	532	533	534	535	536	537	538	539	540	541	542	543	544	545	546	547	548	549	550	551	552	553	554	555	556	Visit 173 - Week 316, Day 2213 or 4 weeks from last visit performed (4 weeks after follow-up) (Internal visit 583)	Visit 777 - Week 320, Day 2241 or 8 weeks from last visit performed (4 weeks after follow-up) (Internal visit 599)			
4th Year Extension	V121	V122	V123	V124	V125	V126	V127	V128	V129	V130	V131	V132	V133	V134	V135	V136	V137	V138	V139	V140	V141	V142	V143	V144	V145	V146					
Week	210	212	214	216	218	220	222	224	226	228	230	232	234	236	238	240	242	244	246	248	250	252	254	256	258	260					
Day	1471	1485	1499	1513	1527	1541	1555	1569	1583	1597	1611	1625	1639	1653	1667	1681	1695	1709	1723	1737	1751	1765	1779	1793	1807	1821					
Visit Numbers (internal use only)	557	558	559	560	561	562	563	564	565	566	567	568	569	570	571	572	573	574	575	576	577	578	579	580	581	582					
5th Year Extension	V147	V148	V149	V150	V151	V152	V153	V154	V155	V156	V157	V158	V159	V160	V161	V162	V163	V164	V165	V166	V167	V168	V169	V170	V171	V172					
Week	262	264	266	268	270	272	274	276	278	280	282	284	286	288	290	292	294	296	298	300	302	304	306	308	310	312					
Day	1835	1849	1863	1877	1891	1905	1919	1933	1947	1961	1975	1989	2003	2017	2031	2045	2059	2073	2087	2101	2115	2129	2143	2157	2171	2185					
Physical examination	X			X			X			X			X			X			X					X		X		X		X	
Urine drug screen & alcohol test																														X	
Pregnancy test (a)	X			X			X			X			X			X			X					X		X		X			
Drug administration	X	X	X	X	X	X	X	X	X	X	X	X	X	X	X	X	X	X	X	X	X	X	X	X	X	X	X				
Adverse Events																														X	
Concomitant meds/Therapies																														X	
Comments																														X	
Vital signs and body measurements																															
Body height																															
Body weight	X						X			X			X			X			X					X		X		X		X	
Body temperature	X						X			X			X			X			X					X		X		X		X	
Blood pressure / Pulse rate	X						X			X			X			X			X					X		X		X		X	
ECG evaluation	X																								X					X	
Safety Laboratory Evaluations:																															
